6.11.4.2 Endpoints Related to Iron

Mean change from baseline and percentage change from baseline are presented for hepcidin, ferritin, TIBC, serum iron, and TSAT, ANCOVA model will be used for treatment comparisons with respect to mean change from baseline in the PEP and SEP.

The proportion of subjects who received any iron therapy and the mean weekly dose of elemental iron will be summarized by route of administration, analysis periods, and treatment groups. The calculation of mean IV (or Oral) weekly dose will include subjects with iron administration and will count only weeks in which a subject was still being followed in the denominator. For proportion of subjects who received each (or both) of the relevant routes of elemental iron, 95% CI for the proportions will be reported along with the difference in proportions as well as the odds ratio; a Mantel-Haenszel method stratified by dialysis organization will be used to calculate the 95% CI for the statistics of treatment comparison. For mean weekly dose of elemental iron, ANCOVA model will be used for treatment comparisons.

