3.5.2 Known Potential Benefits

In studies to date, once-daily oral doses of vadarustat increased mean Hb with fewer excursions above the target range of 10.0 to 11.0 g/dL when compared with darbepoetin alfa. In addition, serum EPO levels remained well below those reported with ESAs in the literature. As a result, there is the potential for the investigational drug vadarustat to provide an effective and safe therapeutic option for the treatment of renal anemia.

In addition, vadarustat may enhance iron absorption, transport, and utilization. Phase 1 and Phase 2 studies have demonstrated a consistent dose-dependent increase in TIBC and decrease in ferritin and hepcidin. Mechanistic studies have demonstrated that HIF stabilization downregulates the iron absorption inhibitor hepcidin, and upregulates the iron-mobilizing regulators ferroportin and transferrin (and its receptor) ([Peyssonnaux 2007](#)). Potential clinical benefits include enhanced erythropoiesis and decreased exogenous iron requirements.

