7.5.2 Iron Supplementation and Phosphate Binders

Investigators will prescribe iron supplementation (IV, oral or intradialytic) as needed throughout the study to maintain ferritin and TSAT according to the Schedule of Activities (SoA) ([Section 1.3](#)). The use of iron-based phosphate binders (e.g., ferric citrate) is permitted.

Important: Subjects already receiving oral iron supplementation as part of their treatment plan may continue their current treatment regimen. Because of the potential for oral iron and phosphate binders to reduce the bioavailability of vadadustat, the trial medication is not to be administered concurrently with an oral iron supplement (including multivitamins containing iron), iron-containing phosphate binders, non-iron-containing phosphate binders, or any oral medications containing iron.

Subjects will be instructed to take any non-iron-containing phosphate binders with a meal at least 2 hours before or 1 hour after the dose of vadadustat. Subjects will be instructed to take iron-containing supplements and phosphate binders at least 1 hour after the dose of vadadustat.

Investigators will prescribe IV iron as needed with dosing according to the dialysis center’s protocol. Iron supplementation details will be captured in the appropriate electronic case report form (eCRF).

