5.3 OTHER EFFICACY ENDPOINTS

Other endpoints include the following:

- Proportion of subjects having a Hb value within the target range (10.0 to 11.0 g/dL) during the primary evaluation period (Weeks 20 to 26).
- Proportion of subjects having a Hb value within the target range (10.0 to 11.0 g/dL) during the secondary evaluation period (Weeks 46 to 52).
- Proportion of subjects having average Hb value within the target range (10.0 to 11.0 g/dL) during the primary evaluation period (Weeks 20 to 26)
- Proportion of subjects having average Hb value within the target range (10.0 to 11.0 g/dL) during the secondary evaluation period (Weeks 46 to 52)
- Mean change from baseline and percentage change from baseline in the primary efficacy period (PEP) and secondary efficacy period (SEP) for iron-related parameters
- Proportion of subject receiving rescue by analysis periods.
- Proportion of subjects receiving RBC transfusions by analysis periods.
- Proportion of subjects receiving ESA medication by analysis periods.
- Time to first rescue by narrow and broad (include any rescue, ESA, and RBC respectively)
- Proportion of subjects who received any IV iron therapy by analysis period)
- Mean weekly IV dose elemental iron by analysis period and route of administration
- Mean change in serum glucose and lipid parameters between Baseline and the PEP (Weeks 20 to 26) and SEP (Weeks 46 to 52)
- Mean change in iron metabolism (including iron, hepcidin, ferritin, transferrin saturation [TSAT], total iron binding capacity [TIBC]) between Baseline and the PEP (Weeks 20 to 26) and SEP (Weeks 46 to 52)

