6.11.4 Other Efficacy Analyses

Except for specifying the analysis population, other efficacy endpoint analyses will be performed using the randomized analysis population.

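### Mean weekly iron dose is compared among iron recipients, a post-randomization subset, so no planned analysis gives the dose difference with a CI over all randomized subjects

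*SAP*

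**What the plan says.** SAP 5.3 lists the endpoint as "Mean weekly IV dose elemental iron by analysis period and route of administration", with no restriction to subjects who received iron. SAP 6.11.4 sets the default: "other efficacy endpoint analyses will be performed using the randomized analysis population".

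SAP 6.11.4.2 then gives the derivation. On subjects: "The calculation of mean IV (or Oral) weekly dose will include subjects with iron administration". On weeks, the calculation "will count only weeks in which a subject was still being followed in the denominator". On the test: "For mean weekly dose of elemental iron, ANCOVA model will be used for treatment comparisons". Nothing in the readable text says that a subject with no iron counts as zero.

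The same section plans a companion analysis: "For proportion of subjects who received each (or both) of the relevant routes of elemental iron, 95% CI for the proportions will be reported", together with the difference in proportions and the odds ratio, stratified by dialysis organization.

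Protocol 7.5.2 describes how iron is given: "Investigators will prescribe iron supplementation (IV, oral or intradialytic) as needed throughout the study". Protocol 3.5.2 states the expected effect: "Potential clinical benefits include enhanced erythropoiesis and decreased exogenous iron requirements".

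**The concern.** Whether a subject receives iron in a period is decided after randomization, by an investigator who knows the treatment in this open-label trial. The protocol expects vadadustat may change that decision. It also reports that vadadustat lowers ferritin, one of the two markers that Protocol Table 1 uses to guide iron supplementation. If treatment changes who receives iron, recipients in the two arms are no longer comparable, and adjusting for baseline covariates does not restore the randomized comparison.

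Zeros are also handled unevenly. The denominator is followed weeks, so an iron-free week counts as zero for a subject who had at least one dose. A subject with no dose in any followed week drops out altogether. Because the summary is by route, a subject who moves from IV to oral iron leaves the IV comparison instead of contributing 0 mg to it.

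At stake is the SAP's dose-level comparison of a benefit that the protocol names. A reader of the report would naturally take the ANCOVA result as the effect of assignment to vadadustat on iron dose.

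**Working it through.** **Inputs.** The plan states no figure for the iron-dose analysis, so there is none to reproduce. The documents give no iron-use rates or doses either. Every rate and dose below is an assumption, chosen to show how the rule behaves.

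**Formula.** Let p be the proportion receiving iron and m the mean weekly dose among recipients, for vadadustat (V) and Mircera (M). The mean over all subjects is p × m, so

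all-subject difference = pV·mV − pM·mM = pM·(mV − mM) + mV·(pV − pM).

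The recipients-only comparison estimates mV − mM. It leaves out the second term, which is the change in use.

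**Simple cases** (mg/week, V minus M):

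| Use V / M | Recipients' mean V / M | Recipients-only difference | All-subject means V / M | All-subject difference |
|---|---|---|---|---|
| 40% / 60% | 50 / 50 | 0 | 0.4×50 = 20 / 0.6×50 = 30 | −10 (10/30 = 33% lower) |
| 40% / 60% | 60 / 50 | +10 | 0.4×60 = 24 / 30 | −6 |
| 50% / 70% | 40 / 50 | −10 | 0.5×40 = 20 / 0.7×50 = 35 | −15 |
| 70% / 70% | 40 / 50 | −10 | 0.7×40 = 28 / 35 | −7 |

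The four rows show, in order, a difference that is missed, reversed, understated, and kept in direction. In the last row use does not differ, and the relative reduction is the same on both scales (10/50 = 7/35 = 20%).

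**When the sign reverses.** Reversal needs mV > mM together with pV·mV < pM·mM, that is 1 < mV/mM < pM/pV. With 40% versus 60% use the upper limit is 0.6/0.4 = 1.5.

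**Simulation of iron need** (2,000,000 draws; need lognormal with median 40 mg/week and log-SD 0.6; iron given when need exceeds a threshold in mg/week; all assumed):

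| Pattern | Use V / M | Recipients' mean V / M | Recipients-only difference | All-subject difference |
|---|---|---|---|---|
| Every need falls by 10 mg/week, threshold 30 | 50.0% / 68.5% | 59.5 / 60.1 | −0.7 | 29.8 − 41.2 = −11.4 |
| Every need falls by 25%, threshold 30 | 50.0% / 68.5% | 52.1 / 60.1 | −8.0 | 26.1 − 41.2 = −15.1 |
| Only low-need subjects stop (threshold 20 on Mircera, 30 on vadadustat) | 68.4% / 87.6% | 60.2 / 52.5 | +7.7 | 41.2 − 46.0 = −4.8 |

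The −0.7 comes from unrounded means. The effect is nearly missed in the first pattern, understated in the second and reversed in the third.

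**The case against.** The strongest reply is that the SAP plans two outputs, not one. In the 40% versus 60% case, the stratified analysis of the proportion receiving iron would report a 20-point difference with its CI. Proportion plus dose among recipients is a recognizable two-part presentation. If both use the same subjects, multiplying them recovers an approximate all-subject mean in each arm. This stands: a reader might infer that an iron-sparing effect would disappear from the report, and the documents do not support that. What remains missing is a CI for the combined quantity, and a rule for reading the two results if they point in opposite directions.

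Second, the tier is low. In the readable text, Protocol 4.4 and 4.8 do not list iron dose. It enters as one of many 'other' endpoints in SAP 5.3, with no margin or decision rule. This also stands.

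Third, the SAP says the calculation will include recipients. It does not say only recipients, and its one 'only' applies to weeks. The randomized-population default might be thought to govern. The restrictive reading is still the natural one, because a sentence naming recipients has little purpose if everyone enters, and a specific derivation does not clearly yield to a general default. If all subjects were intended, the same sentence needs correcting. Appendix A, where further model detail might lie, is largely redacted, so this cannot be settled from the text.

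Fourth, reversal is not the expected result. It needs the pattern in which low-need subjects stop iron; a proportional fall in need only shrinks the difference. Iron is given to ferritin and TSAT targets and by center protocol, so how many subjects would stop is unknown.

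**Conclusion.** The point holds. As written, the dose ANCOVA compares subsets defined by a post-randomization outcome that treatment may change, and it can understate, miss or reverse the difference in mean iron dose. The companion proportion analysis limits the harm but does not supply the all-subject dose difference with a CI.

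The conclusion rests on reading the derivation as restricted to recipients. It holds whether receipt means in that period and route or at any time on study, since both condition on iron use after randomization. The amount of distortion cannot be stated from the documents. In the assumed cases it runs from none in direction (equal use) to a recipients-only +7.7 or +10 mg/week where the all-subject difference is −4.8 or −6.

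A reader might go further and infer that the trial's efficacy conclusion is affected. It is not: the primary and secondary hemoglobin analyses do not use this endpoint.

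**What to change.** In SAP 6.11.4.2, define the variable for the treatment comparison as total elemental iron by the given route divided by followed weeks in the period, with 0 mg for followed weeks without iron. Include all randomized subjects with follow-up in that period. Use a robust or bootstrap CI because many values will be zero. Keep the recipients-only mean as a descriptive summary, labelled as conditional on iron use and read alongside the proportion receiving iron. State whether receipt is judged within the period and route.

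The cost is a sentence or two and one derivation change. No new data are needed, because Protocol 7.5.2 already has iron details recorded in the eCRF. The drawback is a skewed distribution with a mass at zero.

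The change removes selection on iron use, not selection by dropout. Under Protocol 8.1.2, subjects who permanently stop study medication leave the study, and the sample size allows for 30% dropout. The SAP should note that the comparison in later periods still depends on who remains under follow-up.

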6.11.4.3 Other Laboratory Parameters

Mean changes from baseline in PEP and SEP will be summarized by treatment group for serum glucose and lipid parameters – including total cholesterol, LDL, HDL, and triglycerides. ANCOVA model will be used for treatment comparisons.

6.11.4.4 Definition of Rescue

The eCRF collects reasons for ESA medication and RBC transfusion. An Event is considered as rescue only when the event occurred between first dose date to permanent study treatment discontinuation. The series of rescue definitions are defined as follows:

- Narrow:
 - For RBC transfusion, when “Low Hemoglobin” is the reason indicated on the eCRF.
 - For ESA medication:
 - Vadadustat arm: the reason of ESA usage is the subject’s Hb less than 9.0 g/dL.
 - Mircera arm: two scenarios are defined as below:
 - i. the reason of other ESA or Mircera usage is the subject’s Hb less than 9.0 g/dL or Mircera dose increase at least 50%.
 - ii. the reason of other ESA or Mircera usage is the subject’s Hb less than 9.0 g/dL or Mircera dose increase at least 100%.
- Broad:
 - Any RBC transfusion.
 - For ESA medication:
 - Vadadustat arm: any ESA usage.
 - Mircera arm: two scenarios are defined as below:
 - i. Any other ESA usage, or Mircera usage due to the subject’s Hb less than 9.0 g/dL or Mircera dose increase at least 50%.
 - ii. Any other ESA usage, or Mircera usage due to the subject’s Hb less than 9.0 g/dL or Mircera dose increase at least 100%.

6.11.4.4.1 Analysis of Rescue

The number and percentage of subjects receiving rescue by rescue type, treatment group and analysis period will be summarized. Confidence interval will be 95% CI for these proportions along with the difference in proportions as well as the odds ratio. A Mantel-Haenszel test stratified by the dialysis organization will be used to calculate the 95% CI for the statistics of treatment comparison.

Time to first rescue therapy administration by narrow and broad definitions separately will be estimated using the Kaplan-Meier product-limit method and log rank test. Subjects without events will be censored at last dose date. The hazard ratio and corresponding 95% CI for the comparison of vadadustat to Mircera will be estimated using a Cox proportional hazards model, with treatment group, randomization stratification factor (dialysis organization), and baseline Hb as covariates. Kaplan-Meier plots of time to first rescue will be provided.

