There were 266 (15.0%) and 276 (15.6%) subjects that experienced TEAEs resulting in death in the vadadustat and darbepoetin alfa treatment groups, respectively. The most frequent TEAEs by PT resulting in death were similar between both treatment groups, and included cardiac arrest (2.0% and 2.1%), septic shock (1.3% and 1.2%), and cardio-respiratory arrest (1.2% and 1.3%) for the vadadustat and darbepoetin alfa treatment groups, respectively.

In the vadadustat treatment group, all deaths due to TEAEs were considered unrelated. In the darbepoetin alfa treatment group, only 1 death due to TEAE of acute MI was considered related. The TEAEs that resulted in death were similar across both treatment groups.

In addition to Study CI-6548-0017, Study CI-6548-0025, a Phase 2, randomized, open-label study to evaluate vadadustat for the treatment of anemia in hemodialysis subjects converting from epoetin alfa therapy, has recently completed the active patient phase but summary efficacy and data are not available at this time. Subjects who were randomized to vadadustat were treated QD from Day 1 to Week 12 and if Week 12 criteria were met, then vadadustat was administered TIW from Weeks 12 to 20. Dose levels of vadadustat administered in this study include

150, 300, 450, 600, 750 and 900 mg QD or TIW. One hundred twenty-nine subjects were randomized to vadadustat and 36 subjects were randomized to epoetin. All randomized subjects received at least one dose of study drug. Of the randomized subjects, 60.5% of subjects in the vadadustat group and 88.9% of subjects in the epoetin group completed treatment and 76.7% of subjects in the vadadustat group and 94.4% of subjects in the epoetin group completed the study.

Overall, taking into account the entire vadadustat clinical development program, the safety profile to date supports the ongoing clinical development of vadadustat as an orally bioavailable agent for the treatment of anemia associated with CKD.

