6.2 VISIT AND ANALYSIS TIME PERIOD CLASSIFICATION

All assessments will be mapped to the corresponding analysis visit (i.e., target week) based on study day, including unscheduled visits. [Table 1](#) is a general window for each visit based on the protocol. [Table 2](#) will be applied for less frequent assessments such as

[REDACTED] C-Reactive Protein (CRP), Complete Blood Count (CBC) with differential, Serum Chemistry, Lipid Panel, Reticulocyte count, Biomarkers, Erythropoietin and Dialysis Adequacy. All other assessments will apply to the analysis window from Table 1.

If more than one Hb assessment is available in a post-baseline analysis period (i.e., PEP or SEP), then all results will be used to calculate the average of Hb. But if more than one record is available in same day, the last assessment (i.e., at most one record per day) will

be used to calculate the average. For other assessments, if more than one assessment is available in each window, the assessment which is closest to the target day will be used for analysis. If the assessments are equally close, the last assessment will be used.

Table 1. Classification of Assessments at Every Visit (General)

Analysis Time Period	Visit	Target Day	Analysis Window
Baseline	Screening Visit 1	-	-
	Screening Visit 2	-	-
Week 2-6	Baseline	Day 1	<=Day 1 (prior to first dose) ^a
	Week 2	Day 14	Day 1 (post dose) – 21
	Week 4	Day 28	Day 22 – 35
Week 8-16	Week 6	Day 42	Day 36 – 49
	Week 8	Day 56	Day 50 – 70
	Week 12	Day 84	Day 71 – 98
Primary Efficacy Period (PEP) (Weeks 20-26)	Week 16	Day 112	Day 99 – 126
	Week 20	Day 140	Day 127 – 154
	Week 24	Day 168	Day 155 – 175
Week 30-42	Week 26	Day 182	Day 176 – 196
	Week 30	Day 210	Day 197 – 224
	Week 34	Day 238	Day 225 – 252
	Week 38	Day 266	Day 253 – 280
Secondary Efficacy Period (SEP) (Weeks 46-52)	Week 42	Day 294	Day 281 – 308
	Week 46	Day 322	Day 309 – 336
	Week 50	Day 350	Day 337 – 357
Safety Follow-up ^b	Week 52	Day 364	Day 358 – 378 or ET/EOT assessment date + 15 days
	Follow-up	ET/EOT assessment date + 28 days	>= ET/EOT assessment date + 15 days

^a If patient has no first dose date, day 1 will be the randomization date.

^b for Vital Sign, Dialysis Access Type, and Therapeutic Phlebotomy

Table 2. Classification of Assessments for Selected Assessment

Analysis Time Period	Visit	Target Day	Analysis Window
Baseline	Screening Visit 1	-	-
	Screening Visit 2	-	-
	Baseline	Day 1	<=Day 1 (prior to first dose) ^a
Week 2-6	Week 4	Day 28	Day 1 (post dose) – 49

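### Per-period rescue and transfusion percentages take no account of time on treatment, so late-period arm comparisons favour the arm that loses more subjects and periods cannot be compared with each other

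*SAP*

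**What the plan says.** SAP 5.3 lists the proportions with rescue, RBC transfusion and ESA use by analysis period as other efficacy endpoints. For rescue, SAP 6.11.4.4.1 says: "The number and percentage of subjects receiving rescue by rescue type, treatment group and analysis period will be summarized". These are also arm comparisons, with differences in proportions and odds ratios: "A Mantel-Haenszel test stratified by the dialysis organization will be used to calculate the 95% CI for the statistics of treatment comparison". SAP 6.11.4.4.2 applies the same analyses to transfusion. SAP 6.11.4.4.3 is headed ESA rescue, although its first sentence names transfusion.

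Four other provisions bear on how the percentages behave:

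- **Population.** Unless a section says otherwise, "other efficacy endpoint analyses will be performed using the randomized analysis population" (SAP 6.11.4). Section 6.11.4.4.1 names no other population.
- **When an event counts.** "An Event is considered as rescue only when the event occurred between first dose date to permanent study treatment discontinuation" (SAP 6.11.4.4). Under Protocol 8.1.2, a subject who permanently stops study medication does not continue in the study, apart from the early termination visit and a 4-week safety follow-up.
- **Periods.** SAP 6.2, Table 1 defines five post-baseline periods. The first visit window is "Day 1 (post dose) – 21" and the last is "Day 358 – 378 or ET/EOT assessment date + 15 days".
- **Time at risk elsewhere.** For mean weekly iron dose the SAP "will count only weeks in which a subject was still being followed in the denominator" (6.11.4.2). No matching rule is given for the per-period rescue percentages.

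SAP 6.11.4.4.1 also plans Kaplan-Meier, log rank and Cox analyses of time to first rescue, censoring subjects without an event at last dose.

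**The concern.** A subject who stops treatment at Week 10 cannot have a countable rescue in Weeks 30-42 or 46-52. If that subject stays in the randomized denominator, the later tables record no rescue for someone who was not being observed for it. The percentage then mixes two things: how often treated subjects need rescue, and how many subjects are still treated. If one arm loses more subjects, its late percentages fall for the second reason alone.

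Unequal loss is foreseeable. In the earlier 20-week hemodialysis conversion study, "60.5% of subjects in the vadadustat group and 88.9% of subjects in the epoetin group completed treatment" (Protocol 3.4).

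A second, independent problem is that the five periods differ in length. A steady rescue rate would look like a rise and fall over the year.

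Rescue and transfusion use help the reader judge whether hemoglobin was maintained by the assigned drug. A late-period difference produced by unequal follow-up could be taken as a treatment benefit.

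**Working it through.** **Plan's own figure.** The documents give no expected rescue rate and no power for rescue. Their one power figure, above 90% for the hemoglobin comparison, reproduces. With 150 × 0.70 = 105 per arm and SD 1.2, SE = 1.2 × √(2/105) = 0.166. Then 0.75/0.166 − 1.96 = 2.57, or 99.5% power. It is not affected by this point.

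**Step 1: period lengths (SAP Table 1), last day − first day + 1.**

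| Period | Days | Length |
|---|---|---|
| Weeks 2-6 | 1-49 | 49 |
| Weeks 8-16 | 50-126 | 77 |
| Weeks 20-26 | 127-196 | 70 |
| Weeks 30-42 | 197-308 | 112 |
| Weeks 46-52 | 309-378 | 70 |

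The longest is 112/49 = 2.3 times the shortest. If dosing ends at the Week 52 target (Day 364), the last period has only 364 − 309 + 1 = 56 days on treatment. I use 56 below.

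**Step 2: length alone.** Assume a constant rescue hazard h = 0.01 per week and no dropout. The percentage with rescue is 1 − exp(−h × weeks). For 7, 11, 10, 16 and 8 weeks this gives 6.8, 10.4, 9.5, 14.8 and 7.7%. The Weeks 30-42 peak comes only from its length.

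**Step 3: unequal discontinuation, identical rescue hazard.** Assume exponential discontinuation with retention of 60.5% (vadadustat) and 88.9% (Mircera) at Week 52:

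- d = −ln(0.605)/52 = 0.00966 per week for vadadustat
- d = −ln(0.889)/52 = 0.00226 per week for Mircera

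For a period starting s weeks after first dose and lasting L weeks, the percentage of randomized subjects with rescue is exp(−d·s) × h/(h+d) × (1 − exp(−(h+d)·L)).

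| Period | Vadadustat | Mircera | Ratio |
|---|---|---|---|
| Weeks 30-42 (s = 28, L = 16) | 0.763 × 0.509 × 0.270 = 10.5% | 0.939 × 0.815 × 0.178 = 13.6% | 0.77 |
| Weeks 46-52 (s = 44, L = 8) | 0.654 × 0.509 × 0.146 = 4.8% | 0.905 × 0.815 × 0.093 = 6.9% | 0.70 |

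Mean on-treatment time per randomized subject is exp(−d·s) × (1 − exp(−d·L))/d. It is 11.3 versus 14.7 weeks in Weeks 30-42 (ratio 0.77) and 5.0 versus 7.2 weeks in Weeks 46-52 (ratio 0.70). The percentage ratios simply reproduce the ratios of patient-time.

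**Step 4: equal discontinuation.** With 30% lost by Week 52 in every arm, d is the same in each, the formula gives the same percentage in each, and the arm difference is zero. The length artefact remains.

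**Step 5: dependence on the assumed hazard.** For rescue risks of 10% to 50% per 52 weeks with the Step 3 retention, the Weeks 30-42 artefact runs from −0.7 to −4.1 points. The ratios stay near 0.77 and 0.70.

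**Step 6: which remedy works.** Dividing by subjects on treatment at period start (dropping exp(−d·s)) gives 13.7% versus 14.5% in Weeks 30-42 and 7.4% versus 7.6% in Weeks 46-52. That removes most of the arm artefact but leaves the length artefact. A rate per on-treatment patient-week returns 1.0 per 100 in both arms and every period. The crude cumulative percentage to Week 52 has the same defect: with s = 0 and L = 52 it reads 32.6% versus 38.4%. Kaplan-Meier under these assumptions gives 1 − exp(−0.52) = 40.5% in both arms.

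**The case against.** **The planned time-to-event analysis already handles follow-up.** It does so for first rescue over the whole study, because subjects who leave drop out of the risk set, and 6.11.4.4.2 extends it to transfusion. A reader might infer that the SAP ignores time at risk for rescue; that would be wrong. What stands is that this analysis does not correct the per-period tables or their confidence intervals.

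**The SAP does not say that leavers are scored as not rescued.** Correct. This follows from the default population in 6.11.4. The observed-data default for descriptive analyses in 6.3 could be read otherwise, and table specifications are in a separate document. The ambiguity is itself a reason to show how many subjects were on treatment.

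**Arm differences are not inherent in the plan.** Also correct. Period lengths are the same in all arms, and the sample-size section assumes a single 30% dropout rate. The earlier study used daily dosing to Week 12 and moved to three-times-weekly dosing only if criteria were met, so its completion figures may not transfer.

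**Consequences are limited.** These are other efficacy endpoints. No noninferiority margin is given for rescue, and no test of trend across periods is planned. This argues for a modest correction.

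**Conclusion.** The point holds as a reporting weakness with an inexpensive remedy. Under the default denominator, late-period rescue and transfusion comparisons favour whichever arm loses more subjects. In the illustration, arms with identical rescue hazards differ by about 3 points in Weeks 30-42 and 2 points in Weeks 46-52. This rests on an assumed constant hazard of 1% per week, retention levels borrowed from a study of different design, and an assumed exponential timing of loss to Week 52. The non-comparability of periods follows from Table 1 and needs no dropout assumption.

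Two stronger readings are not supported. A reader might infer that a bias toward vadadustat is built in; it appears only if vadadustat subjects discontinue more, and vanishes with equal discontinuation and equal hazards. A reader might also place the 60.5% and 88.9% at Week 20 and obtain a Weeks 46-52 ratio of about 0.40. That requires the same loss rate to continue to Week 52, leaving 0.605^(52/20) = 27% versus 0.889^(52/20) = 74% on treatment. If losses stop at Week 20, the ratio is 0.605/0.889 = 0.68, close to the illustration.

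**What to change.** In SAP 6.11.4.4.1 to 6.11.4.4.3:

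1. Add, for each period and arm, the rescue rate per 100 on-treatment patient-weeks, with a rate ratio or rate difference and its confidence interval. State whether repeat rescues count and, if so, use a variance that allows for them. Read period-specific arm comparisons and time trends from these rates.
2. Show the number of subjects on treatment at the start of each period next to the percentages, and state the denominator.
3. For the cumulative comparison, use the Kaplan-Meier cumulative incidence at Weeks 26 and 52, not the crude percentage of randomized subjects.

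The cost is SAP wording and a few table columns. The dosing and rescue dates are already needed for the rescue definition and the time-to-first-rescue analysis. The on-treatment rates condition on staying on treatment, so they should be labelled descriptive. Like the Kaplan-Meier estimates, they remain open to bias if subjects stop because their anemia is worsening.

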8.1.2 Permanent Discontinuation of Study Medication

Subjects who permanently discontinue study medication prior to study completion will not continue in the study. These subjects are to have their ET visit at the time of permanently discontinuing study medication and perform a 4-week safety follow-up after ET visit.

Subjects may permanently discontinue study medication for any of the following reasons:

- AE
- Investigator's discretion
- Subject withdrawal of consent
- Lack of efficacy
- Lost to follow up despite reasonable efforts by the Investigator to locate the subject
- Death
- Other reasons (pregnancy, kidney transplantation, specific reasons to be documented by the Investigator)

Lack of efficacy is defined as an inadequate response to vadadustat in the Investigator's opinion.

Subjects who undergo a solid organ (including kidney), hematopoietic stem cell, or bone marrow transplantation will have vadadustat permanently discontinued.

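### Permanent stops are censored in the time-to-first-rescue analysis, so one minus the Kaplan-Meier curve overstates the probability of rescue as the SAP defines it

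*SAP*

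**What the plan says.** SAP 6.11.4.4 sets the window for the event: "An Event is considered as rescue only when the event occurred between first dose date to permanent study treatment discontinuation". SAP 6.11.4.4.1 then names the estimator and the censoring rule: time to first rescue, narrow and broad, "will be estimated using the Kaplan-Meier product-limit method and log rank test. Subjects without events will be censored at last dose date". A Cox model follows, and "Kaplan-Meier plots of time to first rescue will be provided". The same section also plans crude figures: "The number and percentage of subjects receiving rescue by rescue type, treatment group and analysis period will be summarized". SAP 6.11.4.4.2 and 6.11.4.4.3 reuse these analyses.

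Protocol 8.1.2 lists the reasons for a permanent stop. They include adverse event, withdrawal of consent, lack of efficacy, loss to follow-up, death and kidney transplantation. Subjects who stop permanently leave the study after an early-termination visit and a 4-week safety follow-up.

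The readable text names no cumulative incidence function and no competing-risk method, and states no assumption of independent censoring for this endpoint. Much of SAP Appendix A is redacted, but the paragraph that governs the analysis is readable.

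**The concern.** Reading one minus Kaplan-Meier as a risk supposes that a censored subject could still have the event later, at the same rate as those who remain. That is reasonable for completers censored at the end of treatment. It is not reasonable for a subject who has died, been transplanted or stopped for good, because SAP 6.11.4.4 rules out any later rescue. What the curve then estimates is rescue in a population where nobody stops, and only if stopping is unrelated to the risk of rescue. The SAP states neither that target nor that condition; its one estimand (SAP 6.11.1) concerns the primary endpoint.

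At stake is how a figure is read. A reader who takes rescue risk at Week 52 from the plot will get a number above the incidence of rescue as defined, with nothing to explain why it exceeds what the crude counts imply.

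**Working it through.** **The plan's own figures.** The documents give no figure for the rescue analysis. The nearest is the 30% drop-out allowance in SAP 3.3, which belongs to the primary test. That statement reproduces: 150 × 0.7 = 105 per arm, 0.75 / (1.2 × √(2/105)) = 4.53, and 4.53 − 1.96 = 2.57, so power is 99.5%, consistent with the stated >90%.

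**Inputs**
- Treatment period: 52 weeks (Protocol 9.1.2).
- Arm size: 150 each (SAP 3.3), so 300 for the combined vadadustat group.
- Stops: 30%, borrowed from SAP 3.3.
- Death alone: 15%, from the 15.0% and 15.6% with fatal events in Study CI-6548-0017 (Protocol 3.4, follow-up time not stated), and 8% as a lower assumption.
- Rescue: assumed, because the documents give no rate.

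**Formulas.** Assume constant, independent hazards over 52 weeks, with a = −ln(1 − p_rescue) and b = −ln(1 − p_stop).
- One minus Kaplan-Meier = 1 − e^(−a) = p_rescue.
- Cumulative incidence of rescue before a stop = a/(a+b) × (1 − e^(−(a+b))).

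**Results**

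| Kaplan-Meier rescue | Stops | Calculation | Incidence | Excess |
|---|---|---|---|---|
| 30% | 30% | 0.500 × (1 − 0.7 × 0.7) | 25.5% | 4.5 points |
| 20% | 30% | 0.385 × (1 − 0.8 × 0.7) | 16.9% | 3.1 points |
| 30% | 15% (death) | 0.687 × (1 − 0.7 × 0.85) | 27.8% | 2.2 points |
| 30% | 8% (death) | 0.811 × (1 − 0.7 × 0.92) | 28.9% | 1.1 points |

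Over assumed rescue risks of 10% to 50%, the excess at 30% stops runs from 1.6 to 7.1 points.

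**Against sampling error.** Under the same hazards, the large-sample (Greenwood) variance of the Kaplan-Meier estimate at 52 weeks is (e^(−a))² × a/(a+b) × (e^(a+b) − 1)/n. At 30% and 30% this is 0.49 × 0.5 × (1/0.49 − 1)/n = 0.255/n. The SE is 4.1 points at n = 150 and 2.9 at n = 300, so 4.5 points is about 1.1 and 1.5 SE.

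**Unequal stops.** In Study CI-6548-0025, "60.5% of subjects in the vadadustat group and 88.9% of subjects in the epoetin group completed treatment", so 39.5% and 11.1% did not. With 30% Kaplan-Meier rescue in both arms, the incidences are 0.415 × (1 − 0.7 × 0.605) = 23.9% and 0.752 × (1 − 0.7 × 0.889) = 28.4%. Simulation agrees: Kaplan-Meier 30.0% against 23.9% observed, and 30.1% against 28.5%.

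**The case against.** **A reader might infer that Kaplan-Meier distorts the gap between arms.** The last example does not show that. The two rescue hazards are equal, and the Kaplan-Meier curves correctly show no gap. The 4.5-point difference (28.4% minus 23.9%) appears only in the cumulative incidence. There it favours the arm with more stops, because those subjects left before they could be rescued, and lack of efficacy is one of the reasons for leaving. Replacing Kaplan-Meier outright could flatter an arm that fails more often. This objection stands.

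**A reader might also infer that the excess is always larger in the arm with more stops.** At similar rescue hazards it is. In absolute points it can reverse: at 39.5% stops a 5% Kaplan-Meier rescue is overstated by about 1.1 points, and an arm with 11.1% stops exceeds that once its rescue passes about 19%, roughly four times the hazard. Unequal hazards are possible, because SAP 6.11.4.4 counts large Mircera dose increases as rescue.

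**Too high depends on the target.** If the target is rescue had nobody stopped, the bias can go down. With a frailty shared between rescue and stopping, a simulation gave Kaplan-Meier 22.7%, incidence before a stop 19.2%, and no-stop risk 26.3%. That limits the claim to rescue as SAP 6.11.4.4 defines it; for that event the direction is fixed.

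**The inputs fit loosely.** The 30% is an allowance for an endpoint at Weeks 20 to 26, not a 52-week stop rate. Study CI-6548-0025 had a different comparator and ran about 20 weeks. Withdrawal and loss to follow-up do not make rescue physically impossible as death does; the definition excludes it.

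**Much is already reported.** Crude percentages come with confidence intervals, and SAP 6.5 analyses time to treatment discontinuation. If everyone else reaches Week 52, the Week 52 cumulative incidence is simply the crude cumulative proportion. The planned percentages are by analysis period, however, and give no cumulative curve.

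**Conclusion.** The point holds for the curve read as a risk. Given the event window in SAP 6.11.4.4 and the censoring rule in SAP 6.11.4.4.1, one minus Kaplan-Meier is never below the probability of rescue as defined, and is above it whenever stops occur. The illustrated excess is 4.5 points at 30% rescue and 30% stops, and 1.1 to 2.2 points with death alone. These sizes rest on assumed rescue rates, constant independent hazards and borrowed stop rates.

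The documents do not support a claim that the log-rank test or the Cox hazard ratio is invalid: both stand as cause-specific comparisons on treatment. Nor do they support a claim that Kaplan-Meier distorts the comparison between arms. Time to first rescue is listed among the other efficacy endpoints (SAP 5.3), so this is a low-cost improvement to reporting and does not bear on the noninferiority conclusion.

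**What to change.** In SAP 6.11.4.4.1, and where 6.11.4.4.2 and 6.11.4.4.3 reuse it:
- Add the Aalen-Johansen cumulative incidence of first rescue, with death, transplant and other permanent discontinuation as competing events, and name it as the curve from which rescue risk is read.
- Plot the competing-event incidence by arm beside it, with lack-of-efficacy stops shown separately.
- Keep the Kaplan-Meier curve, log-rank test and Cox model, and label them cause-specific (on-treatment).

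The cost is a few lines of SAP text and a standard procedure option. Discontinuation dates are already needed for SAP 6.5. The downside is extra curves per figure, and a lower rescue incidence in an arm with more stops must be read together with that arm's competing-event curve.
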